7. REGULATORY AND REPORTING REQUIREMENTS

7.1 **Oversight And Monitoring Plan**

The UWCCC Data and Safety Monitoring Committee (DSMC) is responsible for monitoring data quality and subject safety for all UWCCC clinical studies. A summary of DSMC activities follows:

- Review of all clinical trials conducted at the UWCCC for data integrity and safety
- Review of all serious adverse events requiring expedited reporting as defined in the protocol
- Review of reports generated by the UWCCC data quality control review process
- Submit recommendations for corrective action to the CRC
- Notify the Study Chair of the DSMC's recommendation to the CRC
- Work in conjunction with the Health Sciences IRB in the review of protocol deviations, violations and unanticipated problems reported by the UWCCC DOWGs.
- The committee ensures that notification is provided to all external sites participating in multiple-institutional clinical trials coordinated by the UWCCC of serious adverse events requiring expedited reporting.

7.2 Monitoring And Reporting Guidelines

Investigators will conduct continuous review of data and subject safety at their weekly Phase I/Disease Group meetings where the results of each subject's treatment are discussed and the discussion is documented in the minutes. The discussion will include for each dose level: the number of subjects, significant toxicities as described in the protocol, doses adjustments, and responses observed. Quarterly Protocol Summary Reports (PSR) are required for submission to the Data and Safety Monitoring Committee (DSMC) for review.

7.3 **REVIEW AND OVERSIGHT REQUIREMENTS**

a) Serious Adverse Event – Reported within 7 Days

Serious Adverse Events requiring reporting within 7 calendar days (as described in the protocol) will also be sent to the UWCCC DSMC Chair via email to [contact]. A 7 day "SAE Details" report, generated in the UWCCC database must be attached to the email along with pertinent information regarding the SAE and the UWCCC SAE Routing Form. The Committee Chair will review the information and determine if further action is required. This information is entered and tracked in the UWCCC database.

b) Study Progress Review

Study Progress Review- Protocol Summary Reports

Protocol Summary Reports (PSR) are required to be submitted to the DSMC commensurate with the Phase of the study. The PSR provides a cumulative report of serious adverse events, as well as any protocol violations, deviations or unanticipated problems, toxicities and responses that have occurred on the protocol in the timeframe specified. PSRs are reviewed at each DSMC meeting.

Protocol Summary Reports enable DSMC committee members to assess whether significant benefits or risks are occurring that would warrant study closure. This information is also provided by Disease Oriented Working Group meeting minutes, internal audit and/or response review reports. In addition, the DSMC requires the DOWG or protocol Study Chair to submit external DSMB reports or any other significant study-related information.

In the event that there is significant risk warranting study suspension or closure, the DSMC will notify the PI of the DSMC findings. The DSMC ensures that the PI reports any temporary or permanent suspension of a clinical trial to the sponsor (e.g., NCI Program Director, Industry Sponsor Medical Monitor, Cooperative Group Study Chair, etc.) and other appropriate agencies.

EXPEDITED REPORTING OF SERIOUS ADVERSE EVENTS

Depending on the nature, severity, and attribution of the serious adverse event an SAE report will be phoned in, submitted in writing, or both according to the table below. All serious adverse events must also be reported to the UWCCC Data and Safety Monitoring Committee Chair. All serious adverse events must also be reported to the UW IRB (if applicable), and any sponsor/funding agency not already included in the list.

Determine the reporting time line for the SAE in question by using the following table.

SAE Requiring 7 Day Reporting Occurs at UWCCC:

1. **Report to the UWCCC:**

Reference the **SAE SOP** and the **SAE Reporting Workflow for DOWGs** on the UWCCC website (http://www.uwccc.wisc.edu) for specific instructions on how and what to report to the UWCCC for 7 day reports.

For this protocol, the following entities are required to be notified:

- a) [contact]
- b) Any appropriate parties listed on SAE Routing Form

2. **Report to the IRB:**

Consult the UW-IRB website for reporting guidelines.

3. **Reporting to the FDA**

Serious Adverse Events occurring on studies on which a UW PI is acting as sponsor-investigator must be reported to the FDA within the appropriate time frame. Mandatory and voluntary reporting guidelines and instructions are outlined on the FDA website: http://www.fda.gov/Safety/MedWatch/HowToReport/default.htm

Report the SAE using the FDA Med Watch form available at http://www.fda.gov/downloads/Safety/MedWatch/HowToReport/DownloadForms/UCM082728.pdf.

Expedited reporting requirements for adverse events experienced by patients on arm(s) with						
commerciara	agents only—Arms	I, А, Б, апо С. do 4	Grado 5ª			
Attribution	Gia	ue 4	Graue	5.0		
Auribution	Unexpected	Expected	Unexpected Expected			
	Unexpected	Expected	Olicypeeted	Expected		
Unrelated or Unlikely			7 calendar days	7 calendar days		
Possible, Probable, Definite	7 calendar days		7 calendar days	7 calendar days		
7 Calendar I	Days: Indicates a f	ull MedWatch repor	rt is to be submitted v	within 7 calendar days		
of learning of	f the event.					
a This incluc	les all deaths withir	n 30 days of the last	dose of treatment re	egardless of attribution.		
NOTE: Any death that occurs > 30 days after the last dose of treatment and is attributed possibly, probably, or definitely to the treatment must be reported within 7 calendar days of learning of the event.						
Serious Events: Any event following treatment that results in persistent or significant disabilities/incapacities, congenital anomalies, or birth defects must be reported via MedWatch						

Print the completed Med Watch form and fax it to the FDA.

8. PHARMACEUTICAL INFORMATION: CAPECITABINE

within 7 calendar days of learning of the event.

Other Names: Xeloda

Chemical name: 5'-deoxy-5-fluoro-N-[(pentyloxy) carbonyl]-cytidine.

Molecular Weight: 359.35

Description: Capecitabine is a fluoropyrimidine carbamate with antineoplastic activity. It is an orally administered prodrug of 5'-deoxy-5-fluorouridine (5'-DFUR) which is converted to 5-fluorouracil.

How Supplied: Capecitabine (Xeloda) is supplied as biconvex, oblong film-coated tablets for oral administration. Each light peach colored tablet contains 150 mg capecitabine and each peach-colored tablet contains 500 mg capecitabine.

Solution Preparation: Not applicable.

Route of Administration: Oral.

Availability: Commercial supplies of capecitabine will be used for this study.

Storage and Stability: Store tightly closed at 25 degrees C (77 degrees F); stable for brief periods at 15 to 30 degrees C (59 to 86 degrees F).

8.1 Adverse events and potential risks of Capecitabine (see also tables 1 and 2)

Hand-and-Foot Syndrome: Hand-and-foot syndrome (palmar-plantar erythrodysesthesia or chemotherapy-induced acral erythema) is a cutaneous toxicity (median time to onset of 79 days, range from 11 to 360 days). This is much more commonly observed with capecitabine or infusional 5-FU rather than bolus 5-FU.

Cardiotoxicity: The cardiotoxicity observed with capecitabine includes myocardial infarction/ischemia, angina, dysrhythmias, cardiac arrest, cardiac failure, sudden death, electrocardiographic changes, and cardiomyopathy. These adverse events may be more common in patients with a prior history of coronary artery disease.

Hepatic Insufficiency: Patients with mild to moderate hepatic dysfunction due to liver metastases should be carefully monitored when capecitabine is administered. The effect of severe hepatic dysfunction on the disposition of capecitabine is not known.

Hyperbilirubinemia: In the overall clinical trial safety database of capecitabine monotherapy (N=875), grade 3 (1.5-3 x ULN) hyperbilirubinemia occurred in 15.2% (n=133) and grade 4 (>3 x ULN) hyperbilirubinemia occurred in 3.9% (n=34) of 875 patients with either metastatic breast or colorectal cancer who received at least one dose of capecitabine 1250 mg/m² twice daily as monotherapy for 2 weeks followed by a 1-week rest period. Of 566 patients who had hepatic metastases at baseline and 309 patients without hepatic metastases at baseline, grade 3 or 4 hyperbilirubinemia occurred in 22.8% and 12.3%, respectively. Of the 167 patients with grade 3 or 4 hyperbilirubinemia, 18.6% (n=31) also had postbaseline elevations (grades 1 to 4, without elevations at baseline) in alkaline phosphatase and 27.5% (n=46) had postbaseline elevations in transaminases at any time (not necessarily concurrent). The majority of these patients, 64.5% (n=20) and 71.7% (n=33), had liver metastases at baseline. In addition, 57.5% (n=96) and 35.3% (n=59) of the 167 patients had elevations (grades 1 to 4) at both prebaseline and postbaseline in alkaline phosphatase or transaminases, respectively. Only 7.8% (n=13) and 3.0% (n=5) had grade 3 or 4 elevations in alkaline phosphatase or transaminases. In the 596 patients treated with capecitabine as firstline therapy for metastatic colorectal cancer, the incidence of grade 3 or 4 hyperbilirubinemia was similar to the overall clinical trial safety database of capecitabine monotherapy. The median time to onset for grade 3 or 4 hyperbilirubinemia in the colorectal cancer population was 64 days and median total bilirubin increased from 8 μ m/L at baseline to 13 μ m/L during treatment with capecitabine. Of the 136 colorectal cancer patients with grade 3 or 4 hyperbilirubinemia, 49 patients had grade 3 or 4 hyperbilirubinemia as their last measured value, of which 46 had liver metastases at baseline.

Hematologic: In 875 patients with either metastatic breast or colorectal cancer who received a dose of 1250 mg/m² administered twice daily as monotherapy for 2 weeks followed by a 1-week rest period, 3.2%, 1.7%, and 2.4% of patients had grade 3 or 4 neutropenia, thrombocytopenia or decreases in hemoglobin, respectively. Carcinogenesis, Mutagenesis and Impairment of Fertility: Adequate studies investigating the carcinogenic potential of capecitabine have not been conducted. Capecitabine was not mutagenic in vitro to bacteria (Ames test) or mammalian cells (Chinese hamster V79/HPRT gene mutation assay). Capecitabine was clastogenic in vitro to human peripheral blood lymphocytes but not clastogenic in vivo to mouse bone marrow (micronucleus test).

Reproductive: In studies of fertility and general reproductive performance in mice, oral capecitabine doses of 760 mg/kg/day disturbed estrus and consequently caused a decrease in fertility. In mice that became pregnant, no fetuses survived this dose. The disturbance in estrus was reversible. In males, this dose caused degenerative changes in the testes, including decreases in the number of spermatocytes and spermatids. In separate pharmacokinetic studies, this dose in mice produced 5'-DFUR AUC values about 0.7 times the corresponding values in patients administered the recommended daily dose.

Coagulopathy: See Boxed WARNING regarding interaction with Coumadin in Section 5.2.

Diarrhea: Capecitabine can induce diarrhea, sometimes severe. Patients with severe diarrhea should be carefully monitored and given fluid and electrolyte replacement if they become dehydrated. This is expected to be common for this combination therapy. Necrotizing enterocolitis (typhlitis) has been reported with capecitabine. Toxic deaths have been reported for the combination of oxaliplatin with 5-FU and leucovorin in patients with diarrhea and concomitant neutropenia. Consideration of hospitalizing any such patients should be given.

Drug-Drug Interactions with Capecitabine

Capecitabine (Xeloda) and Coumadin: see boxed warning in Section 5.2

CYP2C9 substrates: Other than warfarin, no formal drug-drug interaction studies between XELODA and other CYP2C9 substrates have been conducted. Care should be exercised when XELODA is co-administered with CYP2C9 substrates.

Phenytoin: The level of phenytoin should be carefully monitored in patients taking capecitabine and phenytoin dose may need to be reduced. Postmarketing reports indicate that some patients receiving capecitabine and phenytoin had toxicity associated with elevated phenytoin levels. Formal drug-drug interaction studies with phenytoin have not been conducted, but the mechanism of interaction is presumed to be inhibition of the CYP2C9 isoenzyme by capecitabine and/or its metabolites.

8.2 Availability

Capecitabine (Xeloda®) is an FDA approved medication and is available by prescription at pharmacies throughout the United States.

9. CORRELATIVE/SPECIAL STUDIES

9.1 Laboratory Correlative Studies

Capecitabine pharmacokinetics: Plasma samples for the analysis of capecitabine and metabolites (5-FU, DFCR, and DFUR) will be obtained at baseline (prior to dosing) and 1, 2, 3, 4, 6, and 8 hours after administration on day 1 and day 9 of cycle 1 and at steady state on cycle 1 days 7 and 15. Plasma and tissue concentrations will be measured by HPLC as previously described.³⁸. For 5FU, the standard curve is linear from 0.019 to 20 μ g/ml, r2 = 0.999, with an intraday variability ranging from 4.49%-5.52% over the standard curve. Inter-day variability over 2 weeks ranges from 4.33-5.42% over the standard curve and the lower limit of quantitation (LLOQ) is 0.0195 μ g/ml. For capecitabine, the standard curve is linear from 0.019 to 20 μ g/ml, r2 = 0.999, with intraday variability ranging from 1.2-7.8% and inter-day variability from 7.6-13.9% over 3 months and a LLOQ of 0.019 μ g/ml. The standard curves for DFCR and DFUR are both linear from 0.625 to 40 μ g/ml, r2 = 0.999, with an intraday variability over 4 weeks ranging from 3.45%-6.36% and 4.24-6.45% and LLOQ of 0.312 μ g/ml and 0.0195 μ g/ml, respectively.

Pharmacokinetic variables will be determined by noncompartmental methods with WinNonlin Pro version 5.2 (Pharsight Corporation, Cary, N.C.). Area under the plasma concentration–time curve is estimated using the trapezoidal rule from time 0 to peak concentration and the log-trapezoidal rule from the peak concentration to the last measurable plasma concentration (AUClast). AUC($0-\infty$) is then calculated from the time of dosing and extrapolated to infinity.

9.2 **PK Sample Collection**

Blood samples are collected in 6-mL EDTA (purple top) tubes at the timepoints described in Table 5, below on day 1, 7, 9 and 15 of cycle 1. Samples are then centrifuged at 3500RPM at 4°C to obtain plasma, aliquotted into cryovials and stored at -70C until analysis.

Time	Time
C1D1	C1D9
0 (prior to first capecitabine dose)	0 (prior to AM capecitabine dose)
1 hr post capecitabine dose	1 hr post capecitabine
2 hr post	2 hr post
3 hr post	3 hr post
4 hr post	4 hr post
6 hr post	6 hr post
8 hr post	8 hr post
C1D7	C1D15
0 (prior to AM dose of capecitabine)	0 (prior to AM capecitabine dose)

10. STUDY CALENDAR

Pre-study evaluations are to be conducted within 2 weeks prior to start of protocol therapy. Scans, x-rays and informed consent must be done ≤ 4 weeks prior to the start of therapy.

	Pre-	C1	C1	C1	C1	C1	C2+	C2+	Off
	Study	Day	Days	Day 8	Day 9	Days 10-	Day 1 ⁱ	Days	Study
		1	2-7			15		2-14	
Capecitabine ^a		Х	Х		Х	Х	Х	Х	
Informed Consent									
	Х								
Demographics	Х								
Medical History	Х								
Concurrent Meds	Х						Х		Х
Physical Exam ^b	Х	Х					Х		Х
Vital Signs	Х						Х		Х
Performance	Х						Х		Х
Status									
CBC, ANC	Х	Xg			Х		X ^h		Х
Chemistries ^c	Х	Xg			Х		X ^h		Х
Pregnancy test ^d	Х								
Adverse Event evaluation	X								X
Tumor	Х						Х		Х
Measurements							(every		
including							2-3		
radiology							cycles)		
assessments ^e							- /		

Pharmacokinetics ^f	Х	Х	Х	Х		
		(day 7)		(day 15)		

- a. See schema for capecitabine dosing
- b. Including height and weight at pre-study evaluation and weight on day 1 of each cycle for first 2 cycles, then every other cycle allowed. If treatment delayed, physical exam may be done at the investigator's discretion.
- c. Na, K, Cl, bicarbonate, BUN, Creatinine, ALT, AST, Alk Phos, Tbili, and albumin.
- d. For premenopausal women only (Postmenopausal women are those who are age >60, or age < 60 who have had oophorectomy or have not had a menses for > 1 year without another etiology for amenorrhea).
- e. Tumor measurements by exam and imaging every 2 -3 cycle per discretion of treating MD. Imaging should include chest (CXR or CT of chest) and abdomen (CT or MRI) with optional imaging for pelvis (CT or MRI) or bones (bone scan or PET) depending on known sites of disease. A PET/CT can be used to replace CT chest, abdomen and pelvis.
- f. See Table 5 for timing of pharmacokinetic blood draws.
- g. Do not need to repeat if done within 1 week prior to course 1 day 1. If done on c1d1 don't use as eligibility labs, use pre-study labs
- h. may be done within 72 hours of each cycle
- i. May be delayed for holidays and unforeseen circumstances

11. MEASUREMENT OF EFFECT

11.1 Antitumor Effect – Solid Tumors

For the purposes of this study, patients should be re-evaluated for response once at 6-9 weeks (+/- 1 week) after initiation of therapy, and then per discretion of treating physician.

Response and progression will be evaluated in this study using the new international criteria proposed by the Response Evaluation Criteria in Solid Tumors version 1.1 (RECIST) Committee [*JNCI* 92(3):205-216, 2000]. Changes in only the largest diameter (unidimensional measurement) of the tumor lesions are used in the RECIST 1.1 criteria.

11.1.1 **Definitions**

Evaluable for toxicity. All patients will be evaluable for toxicity from the time of their first treatment with capecitabine.

Evaluable for Pharmacokinetic Comparison: Patients will be evaluable for the primary endpoint if he or she takes 100% of their capecitabine dose days 1 through 9 and at least 90% of their capecitabine dose days 10 through 15 in cycle one.

Evaluable for objective response. Only those patients who have measurable disease present at baseline who have received at least one cycle of therapy (21)

days) will be considered evaluable for response. These patients will have their response classified according to the definitions stated below.

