1. OBJECTIVES

1.1. **Primary Objective**: To characterize the effect on pharmacokinetic parameters of capecitabine, when dosed using actual versus ideal body weight in obese patients with advanced solid tumors.

1.2. Secondary Objectives:

1.2.1 To characterize the response rate and progression free survival with capecitabine therapy in obese subjects with advanced solid tumors

1.2.2 To determine capecitabine pharmacokinetics in obese patients compared with normal weight historical controls.

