3. PATIENT SELECTION

3.1 Eligibility Criteria

- 3.1.1 Patients must have histologically or cytologically confirmed advanced or metastatic cancer for which capecitabine treatment is considered a standard treatment option.
- 3.1.2 Patients with **measurable or evaluable** disease are eligible
- 3.1.3 Patient's Body Mass Index must be 30 kg/m² or higher.
- 3.1.4 Eastern Cooperative Oncology Group performance status 0-2.
- 3.1.5 Age \geq 18 years.
- 3.1.6 Life expectancy of greater than 12 weeks.
- 3.1.7 Patients must have adequate organ and marrow function as defined below:
 Hematologic: ANC >1000/mcL, Hemoglobin > 8gm/dL (transfusions permitted) and platelets > 75,000/mcL

• Renal: serum creatinine \leq upper limit of normal (ULN) or creatinine clearance (either estimated or calculated) \geq 60 mL/min/1.73 m for patients with creatinine levels above institutional normal.

Females: $Cr_{cl} = (140\text{-}age)(weight in kg)(0.85)$ 72 x Serum creatinine

Males: $Cr_{cl} = (140\text{-age})(\text{weight in kg})$ 72 x Serum creatinine

- Hepatic: Serum Bilirubin ≤ 1.5 x ULN and
 - No liver metastases: AST and ALT \leq 2.5x ULN
 - Liver metastases: AST and $ALT \leq 5x ULN$

- 3.1.8 Ability to understand and the willingness to sign a written informed consent document.
- 3.1.9 Capecitabine is contra-indicated in pregnant women because of known detrimental effects on the fetus. A negative pregnancy test is required in all premenopausal women within 14 days of study therapy initiation. Women of child-bearing potential and men with an active female sexual partner must agree to use adequate contraception (hormonal, surgical, barrier methods or abstinence allowed) prior to study entry and for the duration of study participation. Should a woman become pregnant or suspect she is pregnant while participating in this study, she should inform her treating physician immediately.

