13.4 Analysis of Secondary Endpoints

Responses will be determined using RECIST as described in Section12 and summarized in tabular format. The complete and partial response rates will be calculated and reported along with the corresponding 95% confidence intervals. All eligible subjects (intent-to-treat population) will be included in the calculation of the response rate. Progression-free survival will be analyzed using the Kaplan-Meier method.

PK parameters (based on ideal body weight and actual body weight) of the study participants will be summarized using standard descriptive statistics in terms means, standard deviations and ranges. A two-sample t-test will be used to compare the mean values in the PK parameters in obese patients with normal weight historical controls.

13.5 **Reporting and Exclusions**

13.5.1 **Evaluation of toxicity.** All patients will be evaluable for toxicity from the time of their first treatment with capecitabine.

13.5.2 **Evaluation of response.** All patients included in the study must be assessed for response to treatment, even if there are major protocol treatment deviations or if they are ineligible. Each patient will be assigned one of the following categories: 1) complete response, 2) partial response, 3) stable disease, 4) progressive disease, 5) early death from malignant disease, 6) early death from toxicity, 7) early death because of other cause, or 9) unknown (not assessable due to measurable disease only or insufficient data). [Note: By arbitrary convention, category 9 usually designates the "unknown" status of any type of data in a clinical database.]

All of the patients who met the eligibility criteria (with the possible exception of those who received no study medication) should be included in the main analysis of the response rate. Patients in response categories 4-9 should be considered to have a treatment failure (disease progression). Thus, an incorrect treatment schedule or drug administration does not result in exclusion from the analysis of the response rate.

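### Section 11.1.1 restricts response evaluation to patients with measurable disease and a full cycle, while Sections 13.4 and 13.5.2 count every eligible patient; nothing reconciles the two, and response category 9 is worded backwards

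*Combined protocol and SAP*

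**What the plan says.** Response rate is a named secondary objective (Section 1.2.1): "To characterize the response rate and progression free survival with capecitabine therapy in obese subjects with advanced solid tumors".

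- **Who may enter.** Section 3.1.2 accepts "measurable or evaluable" disease. Section 11.1.2 lists bone lesions, ascites and effusions among the non-measurable kinds, so a patient with no target lesion can enrol.
- **Section 11.1.1.** Evaluable for objective response are "Only those patients who have measurable disease present at baseline who have received at least one cycle of therapy", with a cycle given as 21 days. It continues: "These patients will have their response classified according to the definitions stated below".
- **Section 13.4.** "All eligible subjects (intent-to-treat population) will be included in the calculation of the response rate". Rates are reported with 95% confidence intervals.
- **Section 13.5.2.** The instruction opens "All patients included in the study must be assessed for response to treatment, even if there are major protocol treatment deviations or if they are", and it ends by naming those found not to be eligible. Every patient gets one category. Categories 4 to 9, which include early deaths and unknown status, are failures. The main response analysis covers patients who met eligibility, except possibly those never treated. The closing paragraph bases conclusions on all eligible patients and bars subset analyses from supporting efficacy conclusions.
- **Category 9.** "unknown (not assessable due to measurable disease only or insufficient data".

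**The concern.** Section 11.1.1 gives a response classification to some patients only; Section 13.5.2 gives one to every patient. Both cannot be followed. Two kinds of patient are affected: those with no measurable lesion, and those with measurable disease who die, progress or stop before 21 days. Section 11.1.1 leaves both out, and Section 13.5.2 keeps both in.

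Such patients are foreseeable. Section 3.1.2 admits the first kind. The second kind is ordinary in advanced cancer treated with chemotherapy.

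What is at stake is a response rate whose denominator could be chosen after the data are seen. The 11.1.1 choice leaves out early failures.

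**Working it through.** **1. Do the passages resolve the conflict themselves?** Section 11.1.1 does not call its set a subanalysis set. Sections 13.4 and 13.5.2 never mention it. The subset analyses allowed at the end of Section 13.5.2 exclude patients with major protocol deviations, which is a different criterion. Section 13.4 refers to Section 12 for how response is determined, but Section 12 covers data reporting. The criteria are in Section 11, beside the conflicting rule. So the conflict stands.

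**2. The plan's own figure.** The documents give no expected response rate for this trial. The only stated number the denominator depends on is n = 10 (Section 13.2). It reproduces: for a paired t-test with mean difference 30%, SD 25% and two-sided 0.025, the noncentrality is (30/25) × √10 = 3.79 on 9 degrees of freedom. Power is 84.2%, and 10 is the smallest n reaching 80%, as in Table 13.1. (The text beneath the table states 82%; that is a separate matter.)

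**3. Inputs for the illustration.**
- Eligible patients: n = 10 (Section 13.2). Replacement of patients could make this larger.
- Responders: x = 2, an assumption in line with the single-agent colorectal range of 18.9 to 25.8% in Section 2.3.
- Patients removed by 11.1.1: k = 0 to 5, an assumption; the documents give no figure.
- All responders have measurable disease and at least one cycle, an assumption.

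**4. Formulas.** Section 13.4 rate = x/n. Section 11.1.1 rate = x/(n − k). Gap = xk/[n(n − k)]; with k = 3 this is 6/70 = 8.6 points. Exact (Clopper-Pearson) limits for x responders out of m: the 0.025 quantile of Beta(x, m − x + 1) and the 0.975 quantile of Beta(x + 1, m − x).

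**5. Results with 2 responders.**

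| Removed by 11.1.1 | Rate | Exact 95% CI | Gap from 13.4 (points) |
|---|---|---|---|
| 0 (same as 13.4) | 2/10 = 20.0% | 2.5 to 55.6 | 0 |
| 1 | 2/9 = 22.2% | 2.8 to 60.0 | 2.2 |
| 2 | 2/8 = 25.0% | 3.2 to 65.1 | 5.0 |
| 3 | 2/7 = 28.6% | 3.7 to 71.0 | 8.6 |
| 4 | 2/6 = 33.3% | 4.3 to 77.7 | 13.3 |
| 5 | 2/5 = 40.0% | 5.3 to 85.3 | 20.0 |

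**6. Other responder counts, 3 removed.** One responder: 10.0% against 14.3%. Three: 30.0% against 42.9%. None: 0% under both rules, with the upper limit moving from 30.8% to 41.0%.

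**7. Direction.** Patients lost before 21 days have not reached the first response assessment at 6 to 9 weeks (Section 11.1), so they add to the denominator and not to the responders. Dropping them cannot lower the rate. The direction is less certain for patients without measurable disease. If one of the two responders were such a patient, with a complete response of non-target lesions, removing 3 patients including that one would give 1/7 = 14.3% against 20.0%.

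**The case against.** The strongest reply is that Section 13 governs. Section 13.4 names the population for the rate, Section 13.5.2 repeats it for the main analysis, and the closing paragraph ties conclusions to all eligible patients. Section 11.1.1 sits under definitions and mentions no denominator. On this reading an analyst has one main rate, and early deaths are already failures. Much of this stands, and it is why the all-eligible rate should be kept. It does not remove the conflict: 11.1.1 still says who has a response classified, Section 13.5.2 says everyone does, and the 11.1.1 set has no stated use.

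Several stronger readings are not supported:

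- **Three competing denominators.** A reader might infer a third from the instruction to assess ineligible patients. That instruction concerns assessment; the next paragraph limits the main rate to eligible patients. There are two competing sets.
- **Patients without measurable disease can only fail under Section 13.4.** This is strictly true only for partial response, which needs target lesions. Section 11.1.4.2 defines complete response for non-target lesions, although the overall-response table in Section 11.1.4.3 has no row for patients without target lesions.
- **The shift exceeds the response ranges the protocol quotes.** With 3 or 4 removed it is 8.6 or 13.3 points. That exceeds the width of the colorectal range (25.8 − 18.9 = 6.9 points) but not of the breast range (29 − 15 = 14 points).
- **Category 9 would turn responders into failures.** A patient with measured lesions and a result falls in categories 1 to 4. The wording is an evident slip, and misclassification on that scale is unlikely.

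**Conclusion.** The point holds as an unreconciled conflict between Section 11.1.1 and Sections 13.4 and 13.5.2, with a wording error in category 9. Under the assumptions of 2 responders, all in the 11.1.1 set, among 10 eligible patients, using 11.1.1 instead of Section 13.4 moves the rate from 20.0% to between 22.2% and 40.0% when 1 to 5 patients are removed. If nobody is removed there is no difference. The intervals are wide and overlap heavily, so neither rate would be precise. The harm is a denominator open to choice after the fact, and an upward bias if early failures are dropped.

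A reader might infer that the trial's main result is at risk. It is not: response is secondary and descriptive, and the primary pharmacokinetic comparison and the sample size do not depend on it. The correction is worth making because it is nearly free.

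**What to change.** 1. Keep the all-eligible rate of Sections 13.4 and 13.5.2 as the main response rate, with early death, early stop or no assessment counted as non-response.
2. State in Section 11.1.1 that the measurable-disease set serves only a supportive subanalysis. Delete the one-cycle (21-day) condition, so that treated patients with measurable disease who stop early stay in as non-responders. Report this rate with its 95% CI beside the main rate.
3. Reword the reason in category 9 to *non-measurable disease only or insufficient data*.
4. Point Section 13.4 to Section 11 for the response criteria.

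Example: 2 responders among 10 eligible patients, 2 patients without measurable disease, and 1 with measurable disease who stops before 21 days. The main rate is 2/10 = 20.0% (2.5 to 55.6) and the supportive rate 2/8 = 25.0% (3.2 to 65.1). Section 11.1.1 as it stands would give 2/7 = 28.6%.

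The cost is wording and one extra descriptive rate with a somewhat wider interval. No new data, visits or patients are needed. Making the measurable-disease set the main population would also be possible, but it would reverse the plan's stated choice and is not needed to remove the conflict.
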